APPENDIX 2. CLINICAL SAFETY LABORATORY ASSESSMENTS

Type of Assessment	Details
Hematology	Hemoglobin, hematocrit, platelet count, red blood cell count, white blood cell (WBC) count, and WBC differential
Chemistry	AST, ALT, lactate dehydrogenase (LDH) and isoenzymes 1-5, gamma-glutamyl transpeptidase (GGT), blood urea nitrogen (BUN), creatinine, creatine kinase (CK), myoglobin, aldolase, sodium, potassium, glucose, albumin, total bilirubin
Urinalysis	Dipstick analysis (pH, specific gravity, protein, myoglobin, glucose, ketones, blood, leukocyte esterase, and nitrite)

Table 7: Clinical Safety Laboratory Assessments

ACE-083

APPENDIX 3. CHARCOT-MARIE-TOOTH DISEASE CLASSIFICATION

Inheritance	Pathophysiology	Туре	Example gene associations
Autosomal dominant	Demyelinating	CMTI	PMP22, MPZ, LITAF/SIMPLE, EGR2, NEFL, FBLN5
	Axonal	CMT2	KIFIB, MFN2, RAB7, TRPV4, GARS, NEFL, HSPBI, MPZ, GDAPI,
			HSPB8, DNM2, AARS, DYNCIHI, LRSAMI, DHTKDI, DNAJB2,
			HARS, MARS, MT-ATP6, TFG
	Intermediate	CMTDI	DNM2, YARS, MPZ, IFN2, GNB4
Autosomal recessive	Demyelinating	CMT4	GDAP1, MTMR2, MTMR13 (SBF2), SBF1, SH3TC2, NDRG1,
			EGR2, PRX, HK1, FGD4, FIG4, SURF1
	Axonal	CMT2	LMNA, MED25, GDAP1, MFN2, NEFL, HINT1, TRIM2,
			IGHMBP2, GAN
	Intermediate	CMTRI	GDAP1, KARS, PLEKHG5, COX6A1
X-linked	Intermediate or axonal	CMTX	GJB1, AIFM1, PRPS1, PDK3

Classification and Genetics of CMT Disease¹⁰

APPENDIX 4. MEDICAL RESEARCH COUNCIL MANUAL MUSCLE TESTING GRADING SCALE

Grading Scale for Manual Muscle Testing (MMT)^{11,12}

MMT Grade	Description
5	Normal strength
5-	Uncertain muscle weakness
4+	Inability to resist against maximal pressure throughout range of motion
4	Ability to resist against moderate pressure throughout range of motion
4-	Ability to resist against minimal pressure throughout range of motion
3+	Ability to move through full range of motion against gravity and to resist against minimal pressure through partial range of motion, then contraction breaks abruptly
3	Ability to move through full range of motion against gravity
3-	Ability to move through greater than one half range of motion against gravity
2+	Ability to move through less than one half range of motion against gravity
2	Ability to move through full range of motion with gravity eliminated
2-	Ability to move in any arc of motion with gravity eliminated
1	A flicker of movement is seen or felt in the muscle
0	No contraction palpable

## 1. INTRODUCTION

This statistical analysis plan (SAP) provides a comprehensive and detailed description of strategy and statistical techniques to be used to analyze data for study protocol A083-03. The purpose of the SAP is to ensure the credibility of the study findings by pre-specifying the statistical approaches to the analysis of study data prior to database lock.

## 2. STUDY OBJECTIVES

### 2.1. Primary Objective

#### Part 1

- To evaluate the safety and tolerability of ACE-083 in patients with Charcot-Marie-Tooth (CMT) disease types 1 and X (CMT1 and CMTX)

#### Part 2

- To determine whether treatment with ACE-083 vs. placebo increases total muscle volume of the injected muscle in patients with CMT1 and CMTX

### 2.2. Secondary Objectives

#### Part 1

- To determine the recommended dose level(s) of ACE-083 for Part 2
- To evaluate changes in muscle volume and intramuscular fat fraction of the injected muscle
- To evaluate changes in strength of the injected muscle
- To estimate the systemic exposure of ACE-083 when administered as a local muscle injection
- To evaluate changes in motor function related to the injected muscle
- To evaluate changes in physician-reported and patient-reported outcome measures

#### Part 2

- To determine whether treatment with ACE-083 vs. placebo decreases intramuscular fat fraction of the injected muscle
- To determine whether treatment with ACE-083 vs. placebo increases strength of the injected muscle
- To determine whether treatment with ACE-083 vs. placebo improves motor function related to the injected muscle
- To determine whether treatment with ACE-083 vs. placebo improves physician-reported and patient-reported outcome measures
- To evaluate safety and tolerability of ACE-083

- To estimate the systemic exposure of ACE-083 when administered as a local muscle injection

### **2.3. Exploratory Objectives**

#### **Part 1**

- To evaluate changes in gait parameters
- To evaluate changes in biomarkers

#### **Part 2**

- To evaluate changes in biomarkers
- To evaluate changes in tibialis anterior (TA) compound muscle action potential (CMAP)
- To evaluate changes in gait, activity level, and fall parameters
- To evaluate changes in motor function via the 100-meter timed test

### 3. OVERALL STUDY DESIGN

This study is a two-part multicenter, phase 2 study to evaluate the safety, tolerability, pharmacodynamics (PD), efficacy, and pharmacokinetics (PK) of ACE-083 in patients with CMT1 and CMTX. Part 1 is non-randomized, open-label, dose-escalation and Part 2 is randomized, double blind, placebo-controlled with an open-label extension.

Patients who participate in Part 1 are not eligible to participate in Part 2.

The total study duration for individual patients in Part 1 will be approximately 6 months, which includes a 1-month screening period, a 3-month treatment period, and a 2-month follow-up period after the last dose. The total study duration for individual patients in Part 2 will be approximately 15 months, which includes a 1-month screening period, a 12-month treatment period (6-month double-blind, placebo-controlled followed by a 6-month open-label extension), and a 2-month follow-up period after the last dose.

#### 3.1. Part 1

Part 1 will consist of up to 3 cohorts of patients and will evaluate multiple ascending dose levels of ACE-083 in the tibialis anterior (TA). Patients in each cohort will be enrolled in a 1-month screening period before beginning treatment.

Table 1 below outlines the planned doses to be administered.

**Table 1: Planned Doses to be Administered for Part 1**

Cohort	Dosing Days	Muscle	Planned Dose Level	Type of Administration	ACE-083 n
1	1, 22, 43, 64, and 85	Tibialis Anterior	150 mg	Bilateral	6
2	1, 22, 43, 64, and 85	Tibialis Anterior	200 mg	Bilateral	6
3	1, 22, 43, 64, and 85	Tibialis Anterior	240 mg	Bilateral	6
Total Number of Patients (Planned)					18

Periodic reviews of selected blinded safety and imaging data will be reviewed by the Safety Review Team (SRT) in accordance with the SRT Guidelines.

#### 3.2. Part 2

Prior to the initiation of Part 2, a review of the safety and efficacy data from Part 1 will be done in order to determine the recommended dose level. Up to 40 patients will be enrolled and randomized (1:1 ratio) to receive either ACE-083 (n=20) or placebo (n=20) bilaterally. Patients will receive study drug once every three weeks for approximately 6 months (9 doses). If a patient discontinues the study for reasons other than a safety issue related to investigational study drug and the patient had not completed the Day 43 visit, the patient may be replaced. The replacement patient will receive the same treatment as the patient replaced.

Patients who complete the double-blind treatment period will immediately roll over to open-label treatment with ACE-083. All patients will receive ACE-083 administered at the same dose as in the double-blind period. They will receive bilateral injections, once every three weeks for approximately 6 months (8 doses). In Part 2, the SRT will periodically review the blinded safety data.

A stratified randomization schedule will be prepared under the direction of the Sponsor with the stratification factor of “CMT disease type” (values are CMT1 and CMTX). Because Part 2 is multicenter, an Interactive Response Technology (IRT) system will be used to randomize patients sequentially across clinical sites.

Similar to Part 1, periodic reviews of selected blinded safety and imaging data will be reviewed. Further details concerning the frequency and timing of SRT reviews of Part 2 data are described in the SRT Guidelines.

## 4. STATISTICAL METHODS

### 4.1. General Method

#### 4.1.1. Sample Size Determination

There was no formal sample size calculation for Part 1. Six patients in each cohort will provide sufficient data to evaluate safety and a preliminary assessment of changes in muscle volume and muscle strength.

The sample size calculation for Part 2 is based upon the percent change from baseline in total muscle volume of the injected TA muscle 3 weeks after the last dose. A 10% difference between ACE-083-treated and placebo groups in the percent change in total muscle volume from baseline is considered to be clinically meaningful. The standard deviation (SD) is assumed to be approximately 10% for each group, based on preliminary MRI data for the ACE-083-treated side from the initial TA cohort in Part 1 of the Phase 2 study in FSHD patients.

Assuming a 2-sided type I error rate of 0.10, a 10% difference in percent change from baseline between ACE-083-treated and placebo groups in total muscle volume, a standard deviation of 10% for each group, and a 1:1 randomization, 90% power is achieved with a total sample size of 36 (18 active, 18 placebo), based on a standard t-test.

In addition, this sample size also provides 90% power to detect a 10% difference in 6-minute walk test distance, based on a similar estimated SD of 10% (based off of available data from Part 1 of the Phase 2 study in FSHD patients as well as data from Part 1 of this study, 3-weeks post last dose) and a 2-sided type 1 error rate of 0.10.

In order to account for dropouts (up to 10%), 40 patients will be randomized to study treatment for each muscle (20 active, 20 placebo) to ensure that at least 18 patients per treatment group complete the double-blind treatment period.

#### 4.1.2. Computing Environment

The analysis of clinical data from both Parts 1 and 2 will be performed under the direction of the Acceleron Pharma Biostatistics Department, using SAS® (version 9.4 or higher) and R.

#### 4.1.3. Treatment Description

Treatment descriptions as well as abbreviations used in tables, listings, and figures are described below:

##### Part 1

Unless otherwise stated, tables and figures will be presented as shown below:

Part 1 – Tibialis Anterior

ACE-083 150 mg	ACE-083 200 mg	ACE-083 240 mg	Overall
----------------	----------------	----------------	---------

Listings will contain only the treatment groups shown with no “Overall” group.

**Part 2**

Unless otherwise stated, tables and figures will be presented using one or more of the following as shown below, depending on what is being summarized/analyzed.

Part 2 – Double-blind period

Placebo	ACE-083	Overall
---------	---------	---------

Part 2 – Open-label period – by treatment group sequence

ACE-083→ACE-083	Placebo→ACE-083
-----------------	-----------------

Part 2 – Open-label period – Pooled across treatment group sequence

ACE-083
---------

Listings will contain the treatment groups shown above however, there will be no “Overall” group.

**4.1.4. Definitions of Baseline****Part 1 and Part 2 (Double-blind Phase)**

Baseline is defined to be the last non-missing assessment prior to the first dose of study drug administration. Theoretically, this could be either the Screening assessment or the Day 1 assessment depending on the parameter.

The first dose date will serve as the reference from which the non-missing pre-treatment values would be identified. For patients that are randomized (applicable to patients participating in Part 2) but do not receive any study drug administration, the date of randomization will be the baseline reference.

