Planned Day(s)	-28 to -7	11	8 (±1d)	22 ¹ (±1d)	43 ¹ (±3d)	64 ¹ (±3d)	85 ¹ (±3d)	106 ¹ (±3d)	127 ¹ (±3d)	148 ¹ (±3d)	169 ¹ (±3d)	190 ¹ (±3d)	$\begin{array}{c}(211, 232, \\253, 274)^1\\(\pm 3d)\end{array}$	295 ¹ (±3d)	316 ¹ (±3d)	337 ¹ (±3d)	358 (±3d)	393 (±3d)
Informed consent	Х																	
Inclusion/exclusion criteria	X																	
Urine pregnancy test ³		Х		Х	Х	Х	Х	Х	Х	Х	Х	Х	Х	Х	Х	Х		
Medical history	Х	Х																
MMT assessment (MRC) ⁴	Х											Х		Х			Х	Х
Genetic testing ⁵	Х																	
Full physical examination ⁶	Х							Х				Х		Х			Х	Х
Limited physical examination ⁷		Х		Х		Х			Х	Х	Х		Х		Х	Х		
Injection site examination ⁸		Х	Х	Х	Х	Х	X	Х	Х	Х	Х	Х	Х	Х	Х	Х		
Vital signs ⁹	Х	Х	Х	Х	Х	Х	Х	Х	Х	Х	Х	Х	Х	Х	Х	Х	Х	
Hematology ¹⁰	Х	Х		Х	Х	Х	Х	Х		Х		Х	Х	Х		Х	Х	
Chemistry ¹⁰	X	Х		Х	Х	Х	Х	Х		Х		Х	X	Х		Х	Х	
Urinalysis ¹⁰	Х	Х			Х	Х	Х	Х		Х		Х	Х	Х		Х	Х	
Biomarkers ¹¹	Х	Х		Х	Х	Х	Х	Х		Х		Х	Х	Х		Х	Х	Х
Anti-drug antibody		Х	Х	Х	Х	Х	Х	Х		Х		Х	Х	Х		Х	Х	X ¹²
Serum PK ¹³		0, 1, 2, 4, 6 h	Х				0, 1, 2, 4, 6 h					Х		Х			Х	Х
ECG (12 lead)	Х	$4 h^{14}$					$4 h^{14}$											
Bilateral MRI ¹⁵		Х			Х			Х				Х		Х			Х	Х
Timed function tests ¹⁶	X	Х		Х	Х	Х	Х	Х		Х		Х	X	Х		Х	Х	Х
Balance and gait tests ¹⁷	Х	Х						Х				Х		Х			Х	Х
Strength tests ¹⁸	X	Х	Х	Х	Х	Х	Х	Х		Х		Х	Х	Х		Х	Х	Х
CMTES2 ¹⁹	X	Х						Х				Х		Х			Х	Х
CMT-HI ¹⁹	Х				Х			Х		Х		Х		Х			Х	Х

Table 6: Schedule of Events for Part 2: Randomized, Double-Blind, Placebo-Controlled with Open-Label Extension

09 January 2019

CMAP of tibialis anterior

Х

Х

Х

Clinical Study Protocol Study A083-03 Revision: 03

	Screening				Double	Blind, Pl	acebo-Cont	rolled					Open	-Label			ET ²	EOS ²³
Dose(s)		1		2	3	4	5	6	7	8	9	10	11, 12, 13, 14	15	16	17		
Planned Day(s)	-28 to -7	1^1	8 (±1d)	22 ¹ (±1d)	43 ¹ (±3d)	64 ¹ (±3d)	85 ¹ (±3d)	106 ¹ (±3d)	127 ¹ (±3d)	148 ¹ (±3d)	169 ¹ (±3d)	190^{1} (±3d)	$(211, 232, 253, 274)^1$ (±3d)	295 ¹ (±3d)	316 ¹ (±3d)	337 ¹ (±3d)	358 (±3d)	393 (±3d)
Monitoring of concomitant medications	Х	Х	Х	Х	Х	Х	Х	Х	Х	Х	Х	Х	Х	Х	Х	Х	Х	Х
Monitoring of adverse events		Х	Х	Х	Х	Х	Х	Х	Х	Х	Х	Х	Х	Х	Х	Х	Х	Х
Randomization ²⁰		Х																
Distribution of PAMSys TM Device ²¹	Х																	
Study drug administration ²²		Х		Х	Х	Х	Х	Х	Х	Х	Х	Х	Х	Х	Х	Х		

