¹⁵ MRI assessments should be completed within 5 days prior to the scheduled dose administration, with the exception of the Day 1 MRI which may be completed within 14 days prior to Day 1 visit. MRI assessments during the follow-up period (Day 358/ET and Day 393/EOS) have a ± 5 day window.

¹⁶ 10-meter walk/run, 6-minute walk, 100-meter timed test (Part 2, open-label only; starting at the Dose 10 visit and continuing through to the EOS visit at all timepoints noted). Tests may be performed within 3 days prior to Day 1 visit.

¹⁷ Gait parameters, Berg balance scale. Tests may be performed within 3 days prior to Day 1 visit.

¹⁸ Maximum voluntary isometric contraction testing will be conducted using a handheld dynamometer. Both sides will be tested (right and left).

¹⁹ CMTES2 to be assessed by investigator; CMT-HI to be completed by patient

²⁰ Randomization should occur within 24 hours prior to Day 1 dose.

²¹ PamSysTM device is a physical activity monitoring system that will be worn by the patient for the duration of the study.

²² Study drug administration should occur within 21 days (\pm 3 days) of the previous dose.

²³ If subjects enroll directly into a separate extension study and will receive additional treatment with ACE-083, they do not need to complete the EOS visit. For these subjects, their final Study Visit in this protocol will be the ET visit.

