##### 4.7.2.2.1. Double-Blind Period

###### Muscle Strength (MVIC)

Individual MVIC data will be listed.

Descriptive statistics of the raw data as well as the absolute and percent change from baseline will be provided by side treated [left and right]. The average absolute and average percent change from baseline for the left and right sides will also be provided.

A plot of the mean ( $\pm$  SEM) of the average percent change from baseline for the left and right sides by scheduled day and treatment group will also be provided.

An ANCOVA model will be fitted in order to assess the effect of ACE-083 on the average percent change from baseline for the left and right side at Day 190 with the following covariates: TREATMENT, MRC-MMT DECIMAL SCORE, BASELINE, CMT-TYPE where:

- TREATMENT represents the treatment group (ACE-083 or placebo)
- MRC-MMT DECIMAL SCORE represents the conversion of the screening MRC-MMT grade to the decimal version as follows: 5 = 5.0, 5- = 4.67, 4+ = 4.33, 4 = 4.0, 4- = 3.67, 3+ = 3.33, 3 = 3.0, 3- = 2.67, 2+ = 2.33, 2 = 2.0, 2- = 1.67, 1+ = 1.33, 1=1.0
  - This quantity will be the average from the left and right sides and will be computed for each individual patient.
- BASELINE represents the baseline MVIC (average of left and right sides)
- CMT-TYPE refers to the type of CMT (e.g. CMT1 or CMTX)

The effect of ACE-083 versus placebo will be estimated using the ANCOVA model described above and tested using a 0.1 significance level (2-sided). The least-square mean estimate along with the corresponding 90% confidence interval will be provided. In addition, the 95% confidence interval will also be provided. A bar chart of the least squares mean  $\pm$  SEM of the percent change from baseline will be provided.

If the Day 190 MVIC assessment has no missing data, then the above ANCOVA model will be used for analysis. If missing data is present, a standard multiple imputation with the above ANCOVA model will be used for analysis as described in Section 4.11.1.

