## 6-Minute Walk Test

Individual data will be listed.

Descriptive statistics of raw data as well as changes from baseline (absolute and percent change) will be provided by treatment group by scheduled time separately for cumulative distance recorded at 1 minute, 2 minutes, 3 minutes, 4 minutes, 5 minutes, and 6 minutes. A plot of mean  $\pm$  SEM for the cumulative distance recorded at 6 minutes will also be provided for the percent change from baseline for each treatment group.

An ANCOVA model will be fitted in order to assess the effect of ACE-083 on the Day 190 percent change in the cumulative distance recorded at 6 minutes. Covariates to be included in the model are TREATMENT, HEIGHT, CMT-TYPE, and BASELINE where HEIGHT refers to the height of the patient (cm) and BASELINE represents the baseline distance walked in 6 minutes and each of the other covariates are defined the same as what was described for MVIC.

The effect of ACE-083 on the Day 190 percent change in the cumulative distance recorded at 6 minutes from baseline versus placebo will be estimated using the ANCOVA model described above and tested using a 0.1 significance level (2-sided). The least-square mean estimate along with the corresponding 90% confidence interval will be provided. In addition, the 95% confidence interval will also be provided as well as a bar chart of the least squares mean estimates ( $\pm$  SEM) for each of the treatment groups.

An ANCOVA model will also be fitted in order to assess the effect of ACE-083 on the Day 190 absolute change in the cumulative distance recorded at 6 minutes from baseline data. Covariates to be included in the model are TREATMENT, HEIGHT, CMT-TYPE, and BASELINE where HEIGHT refers to the height of the patient (cm) and BASELINE represents the baseline distance

walked in 6 minutes and each of the other covariates are defined the same as what was described for MVIC.

The effect of ACE-083 on the Day 190 absolute change in the cumulative distance recorded at 6 minutes from baseline versus placebo will be estimated using the ANCOVA model described above and tested using a 0.1 significance level (2-sided). The least-square mean estimate along with the corresponding 90% confidence interval will be provided. In addition, the 95% confidence interval will also be provided as well as a bar chart of the least squares mean estimates ( $\pm$  SEM) for each of the treatment groups.

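### Strength, walking, balance and CMTES2 are measured twice before dosing, but the Part 2 models use only the last value: a cheap gain in precision is left unused

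*SAP*

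**What the plan says.** The Part 2 schedule (Protocol Appendix 1, Table 6; repeated in SAP Appendix 1) marks the rows "Timed function tests", "Balance and gait tests", "Strength tests" and CMTES2 at both Screening (Day -28 to Day -7) and Day 1. The timed tests are the 10-meter walk/run and the 6-minute walk. The balance and gait row covers Berg and the gait parameters.

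SAP 4.1.4 states: "Baseline is defined to be the last non-missing assessment prior to the first dose of study drug administration". For these measures that is normally Day 1, and Screening serves only when Day 1 is missing.

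Each Day 190 model in SAP 4.7.2.2.1 then carries one baseline of its own measure. For 6MWD, "Covariates to be included in the model are TREATMENT, HEIGHT, CMT-TYPE, and BASELINE", and "BASELINE represents the baseline distance walked in 6 minutes". The models for MVIC, 10-meter walk/run, Berg, CMTES2 and mid-swing foot angle are built the same way. Where an MMRM is planned (MVIC, 10-meter walk/run, 6MWD), it reuses the ANCOVA covariates.

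The Screening readings do have other uses. Protocol 14.2.3 takes the screening-to-baseline change in strength as the Part 1 control, and SAP 4.2 uses Screening 6MWD to decide Per Protocol membership. SAP section 5 does not discuss the choice of baseline covariate.

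**The concern.** Walk tests and hand-held dynamometry vary from visit to visit. Two readings taken before randomisation generally predict Day 190 better than one, and a better predictor narrows the confidence interval for the treatment effect. These measures are what would show whether added muscle volume brings strength or function, and 6MWD has its own power statement (SAP 4.1.1). With about 18 completers per arm, precision is scarce, and the second reading is already being collected. At stake is the width of the 90% intervals on the named secondary endpoints.

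The measures outside this point are total muscle volume and fat fraction (one pre-dose MRI), CMT-HI and MRC-MMT grade (Screening only), and the falls model (no baseline fall count).

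**Working it through.** **The plan's own figure.** The inputs from SAP 4.1.1 are a difference of 10%, SD 10%, 18 per arm and two-sided alpha 0.10. The noncentrality is 10 / (10 × √(2/18)) = 3.0 on 34 df, which gives t-test power of 90.2%. Then 36 / 0.90 = 40 randomised. The statement reproduces.

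**Gain from the second reading.** Let ρ be the correlation of each pre-dose reading with Day 190, and τ the Screening–Day 1 correlation. Both are assumptions, because the documents give neither. Suppose Screening predicts Day 190 as well as Day 1 does. Residual variance is then proportional to

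- 1 − ρ² with one reading
- 1 − 2ρ²/(1 + τ) with both

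Example with ρ = τ = 0.8: 1 − 0.64 = 0.360, and 1 − 1.28/1.8 = 0.289, a ratio of 0.802.

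To express this as 6MWD power, hold the SD of the change at 10%. The residual SD with one reading is then 10 × √((1 + ρ)/2), and with both it is that value times the square root of the ratio. The table uses 18 per arm and 31 residual df. The τ values are ρ itself and the midpoint between ρ and 1.

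| ρ | τ | Variance ratio | Power, one reading | Power, both |
|---|---|---|---|---|
| 0.5 | 0.5 | 0.889 | 95.9% | 97.4% |
| 0.5 | 0.75 | 0.952 | 95.9% | 96.6% |
| 0.7 | 0.7 | 0.830 | 93.8% | 96.8% |
| 0.7 | 0.85 | 0.922 | 93.8% | 95.2% |
| 0.8 | 0.8 | 0.802 | 92.6% | 96.5% |
| 0.8 | 0.9 | 0.906 | 92.6% | 94.6% |
| 0.9 | 0.9 | 0.776 | 91.4% | 96.2% |
| 0.9 | 0.95 | 0.891 | 91.4% | 93.9% |
| 0.95 | 0.95 | 0.763 | 90.8% | 96.1% |
| 0.95 | 0.975 | 0.883 | 90.8% | 93.5% |

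The cut in variance is therefore about 5% to 24%, and it is zero at τ = 1. At ρ = 0.9 the 90% half-width falls from 5.51 points to 4.85 (τ = 0.9) or 5.20 (τ = 0.95).

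**Cost of the extra covariate.** With 36 patients, chance imbalance inflates the expected variance of the treatment effect by (36 − 3)/(36 − 3 − q) for q covariates besides treatment. The 6MWD model has q = 3, giving 33/30. Adding Screening gives 33/29, which is 30/29 = 1.034 times as large. Net ratios over the table run from 0.763 × 1.034 = 0.789 to 0.952 × 1.034 = 0.985. With this cost and the lost degree of freedom included, the power gain runs from 0.3 to 5.5 points.

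**If Screening predicts less well than Day 1.** Take Day 1–Day 190 at 0.80, τ = 0.90 and Screening–Day 190 at r. The explained share is (0.64 + r² − 2 × 0.80 × 0.90 × r)/(1 − 0.81).

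- r = 0.77: 0.1241/0.19 = 0.653; residual 0.347 against 0.360, a cut of 3.7%
- r = 0.75: 0.1225/0.19 = 0.645; residual 0.355, a cut of 1.3%
- r = 0.72: 0.1216/0.19 = 0.640; no cut

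Set against the 3.4% cost, r = 0.77 is about break-even and the other two are small net losses.

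**Simulation of the percent-change ANCOVA.** The assumptions were mean 370 m, CV 25%, ρ = 0.92, Screening limited to 150–500 m, and no height or CMT type in the model. The empirical SE of the effect, Day 1 only against Screening added, was:

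- τ = 0.92: 3.93 against 3.57, variance ratio (3.57/3.93)² = 0.825
- τ = 0.96: 3.98 against 3.79, ratio 0.907
- τ = 0.99: 3.91 against 3.92, ratio 1.005

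Estimates stayed near the true 10% throughout. The simulated SD of percent change was about 11%, so only the relative SEs are used here.

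**The case against.** A last-pre-dose baseline is conventional and clearly stated. The 6MWD power statement rests on an unadjusted t-test and holds, and the planned ANCOVA already adds baseline, height and CMT type. Any loss is therefore relative to a better model, not to what the plan promises. That stands.

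The size is also open to challenge. Readings one to four weeks apart may well correlate more strongly than readings 27 weeks apart, and the older reading may predict Day 190 less well. Either pulls the gain towards zero. This stands too, and it is why the gain is given as a conditional range.

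MVIC probably gains less than the others. It is already the maximum of three trials per side, averaged over two sides (SAP 4.7.1.1 and 4.7.2.2.1), and its model already holds the screening MRC-MMT score, although that is a different instrument. Berg and CMTES2 are bounded scores analysed as absolute change, so the percent-change simulation does not speak to them. Mid-swing foot angle is a gait measure and hence exploratory.

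Screening 6MWD is the eligibility value, so it is truncated and may shift by Day 1 through practice or regression to the mean. Because it precedes randomisation, this does not bias the treatment comparison. It is a reason to use it as a covariate and not in the change score.

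**Conclusion.** The point holds as a cheap improvement. For MVIC, 6MWD, 10-meter walk/run, Berg and CMTES2, and for the exploratory gait measures, a pre-randomisation reading of the same variable goes unused in Part 2. If Screening predicts Day 190 about as well as Day 1 does, using it cuts residual variance by roughly 5% to 24% and adds about 1 to 5 points of 6MWD power at the SAP's 10% SD. If it adds nothing, the result is a variance increase of about 3%. All of this rests on assumed correlations.

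A reader might infer that 6MWD is underpowered as planned, that the analysis is biased, or that a definite number of patients is being wasted. The documents support none of these. The 90% figure reproduces, a single pre-dose covariate leaves the randomised comparison valid, and no correlation is given from which a patient equivalent could be fixed. Nor does the point reach the primary endpoint.

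**What to change.** In SAP 4.7.2.2.1, keep Day 1 as the reference for change. Add SCREENING, the Screening value of the same variable (left-right average where applicable), as a covariate in the Day 190 ANCOVA for MVIC, 6MWD, 10-meter walk/run, Berg, CMTES2 and, as exploratory, mid-swing foot angle. Add it to the MMRM for the three measures that have one. If one pre-dose value is missing, substitute the other. SAP 4.11.1 should say whether Screening is among the time points used for imputation; where it is in the analysis model, it should be.

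Do not average the two readings or change the percent-change denominator. Averaging does well if both readings predict equally, but it loses if Screening is informative only through Day 1. With ρ = 0.8 and τ = 0.9, Screening–Day 190 is then 0.72, the mean's covariance with Day 190 is 0.76 and its variance is 0.95. The residual is 1 − 0.5776/0.95 = 0.392 against 0.360, a ratio of 1.089. With ρ = 0.9 and τ = 0.95 the ratio is 1.107.

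Part 1 made the same assessments at Screening and Day 1, so the sponsor can estimate the correlations there and settle the model before unblinding. Part 1 follows patients to Day 141, so its later correlations only approximate those at Day 190. The cost is SAP wording and one residual degree of freedom per model, with no new data.
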